9.1.2.4 PSL interaction on CBD (Part B)

The log-transformed PK parameters ($C_{max,ss}$, AUC_{τ}) of CBD and its metabolite, and the metabolite to parent ratio based on AUC_{τ} (no transformation required) will be analyzed by the model specified in [Section 9.1.2](#), where period includes Treatment Periods 4 and 5 and treatment includes CBD+PSL and CBD+Placebo, to assess the effects of PSL on CBD.

Point estimates for the ratio of geometric means with and without PSL (CBD+PSL vs CBD+Placebo) and the respective 2-sided 90% CIs will be computed using the least squares means and the root mean squares of error from the mixed effects model, based on the log-transformed data with subsequent exponential transformation.

10 PHARMACODYNAMICS

Pharmacodynamic parameters (absolute values and change from Baseline) will be summarized by phase, treatment, phase day and timepoint using the FAS. Figures of summaries and individual assessments will be based on the FAS.

The PD parameters include:

- Smooth Pursuit Eye Movements
- Body Sway
- VAS Mood and Alertness (Bond & Lader)
- VAS feeling high, internal and external perception (Bowdle)
- Saccadic eye movements
- Adaptive tracking
- VAS alcohol intoxication (Part A only)

For the derivation of VAS feeling high, internal and external perception (Bowdle) and VAS Mood and Alertness (Bond & Lader) see [Appendix 14.1](#) and [Appendix 14.2](#) respectively. The raw values of VAS alcohol intoxication will be presented, and any derivation required will be outlined in CSR.

10.1 Analysis of pharmacodynamics variables

Pharmacodynamic parameters will be analyzed separately for each study part.

10.1.1 Descriptive figures and summaries

The PD parameters (absolute values and changes from baseline) will be summarized by phase, treatment and timepoint using descriptive statistics (number of available observations [n],

arithmetic mean, median, SD, minimum, maximum, geometric mean, geometric CV and 95% CI for the geometric mean [assuming lognormally distributed data]).

Individual participant profiles of PD parameters over time will be generated using the FAS.

Graphs of the Least Squares Means estimates over time by treatment will be presented with 95% confidence interval (CI) as error bars.

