9.4 Planned pharmacodynamic analyses

All PD parameters (raw values, change from Baseline, and percentage change from Baseline) and variables will be listed and summarized by study part and treatment with mean, median, standard deviation (SD), minimum and maximum for the PD-PPS.

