3 DATA ANALYSIS CONSIDERATIONS

3.1 General presentation of summaries and analyses

Each study part will be summarized and analyzed separately.

Statistical evaluation will be performed by ICON PLC with the exception of PD which will be conducted to UCB. The datasets will follow the UCB analysis data model (ADaM) data specifications.

All analyses will be performed using SAS version 9.4 or higher (SAS Institute, Cary, North Carolina, United States). The PK noncompartmental analysis (NCA) will be performed using Phoenix WinNonlin®v6.3 or higher (Certara L.P., Princeton, NJ, USA) for pharmacokinetics parameters estimation. All non-PD TFLs will be produced by ICON PLC SAS programming (Early Phase).

Continuous variables will be summarized by phase (defined in [Section 3.5](#)), treatment and timepoint (where applicable) including number of study participants (n), mean, standard deviation (SD), median, minimum, maximum and 95% confidence intervals (CI) for the mean. Geometric coefficient of variation (geoCV), geometric mean and 95% confidence interval (CI) for the geometric mean will also be presented in the descriptive statistics for the PK concentration data and PK parameters of; PSL and its metabolites () and

██████████), and CBD and its active metabolite. In all outputs the confidence limits will be restricted to the possible values that the variable can take.

Categorical variables will be summarized by phase, treatment and timepoint (where applicable) with frequency counts and percentages.

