3.3 Definition of Baseline values

Measurement-specific Baseline timepoints are presented in Table 3–1.

Table 3–1: Definition of Baseline

Measurement	Definition of Baseline
Hematology, serum chemistry, urinalysis	
For Part A, baseline is defined as the visit at which study participants were randomized to one of the four treatment sequences i.e. Day -1 prior to Treatment Period 1.
 
For Part B, baseline is defined as Day -1 prior to Treatment Period 2.
 
For both study parts, if Day -1 is missing or multiple assessments occur, the last measure prior to dosing will be used.

Vital Signs	
For Part A, baseline is defined as predose on Day 1 of Treatment Period 1.
 
For Part B, baseline is defined as predose on Day 1 of Treatment Period 2.
 
For both study parts, if predose on Day 1 is missing or multiple assessments occur, the last measure prior to dosing will be used.

ECG	
For Part A, the mean of the last three measurements predose on Day 1 of Treatment Period 1 will be taken as baseline.
 
For Part B, the mean of the last three measurements predose on Day 1 of Treatment Period 2 will be taken as baseline.
 
For both study parts, if less than three replicates are available predose, the mean of the available replicates (predose) will be taken as baseline.

C-SSRS	For both study parts, separate baseline questionnaire for C-SSRS.

Measurement	Definition of Baseline
PD variables	For both study parts, baseline for change from baseline summaries and tables is defined as the average of the two values measured at predose of given day. Baseline definition for the model is defined in Section 10.1.2 .

The change from Baseline to any subsequent post-Baseline visit will be calculated as the simple difference between that post-Baseline visit's value and the Baseline visit value, as below:

$$\text{Post Baseline Visit Value} - \text{Baseline Visit Value}$$

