4.2.1 Pharmacokinetics

The 95% CI lower and 95% CI upper should be left blank if the SD (or equivalently, the geometric CV) is 0. Measurements of PK concentrations that are below the limit of quantification (BLQ) and which are occurring prior to t_{max} will be imputed with half of the lower

limit of quantification (LLOQ/2), except for embedded BLQ values (between two measurable data points) which will be treated as missing, for the purpose of calculating the geometric mean and its 95% CI, the geometric CV, the arithmetic mean and SD for summaries and figures. Post- t_{max} , BLQ values will be treated as missing. Descriptive statistics of concentrations will be calculated if at least 2/3rd of the individual data points are quantifiable (\geq LLOQ).

For all individual PK concentration figures any concentrations that are BLQ will be regarded as missing, with the exception of predose BLQ measurements which will be imputed with “LLOQ/2” for linear scale plots.

The following rules will apply for PK data listings and summaries:

- Values below the LLOQ will be reported as “(BLQ)” in the listings
- Descriptive statistics of plasma and dried blood concentrations will be calculated if more than 2/3rd of individual data points are quantifiable (\geq LLOQ) at the given time-point. Values that are BLQ will be replaced by the numerical value of the LLOQ/2 in this instance.

However, if $n < 3$, then only n , minimum and maximum will be presented, and the median will also be presented if $n = 3$. The other descriptive statistics will be left blank.

- For t_{max} , only N , median, minimum and maximum will be displayed into the summary statistics
- For plasma concentrations, all BLQ values occurring prior to t_{max} will be replaced by “LLOQ/2”, except for embedded BLQ values (between two measurable data points) which will be treated as missing. Post- t_{max} , BLQ values will be treated as missing. The Pharmacokinetic analysis will be performed in accordance to the Guideline on performing NCA analysis dated 08 Nov 2017.
- For the individual figures, any concentrations that are BLQ will be regarded as missing, with the exception of predose BLQ measurements which will be imputed with “LLOQ/2” for linear scale plots.
- If no study participants have data, only $n=0$ will be presented. The other descriptive statistics will be left blank.
- The geometric CV will be calculated using the following formula where SD is the standard deviation from the log-transformed data:

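### SAP 10.1.1 prescribes geometric statistics for PD changes from baseline, where zero or negative values leave them undefined; only those descriptive cells are affected

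*SAP*

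**What the plan says.** SAP 10.1.1 applies a single list of statistics to two kinds of PD data: "The PD parameters (absolute values and changes from baseline) will be summarized by phase, treatment and timepoint using descriptive statistics". After the number of observations, the list reads "arithmetic mean, median, SD, minimum, maximum, geometric mean, geometric CV and 95% CI for the geometric mean [assuming lognormally distributed data". No PD variable is excepted, and changes are treated in the same way as absolute values.

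SAP 3.3 fixes what a change is: "The change from Baseline to any subsequent post-Baseline visit will be calculated as the simple difference between" the post-baseline and baseline values. For PD, "baseline for change from baseline summaries and tables is defined as the average of the two values measured at predose of given day".

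The only formula for a geometric CV is in the PK section, SAP 4.2.1: "The geometric CV will be calculated using the following formula where SD is the standard deviation from the log-transformed data".

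Two other places describe PD or general summaries differently:
- SAP 3.1 sets n, mean, SD, median, minimum, maximum and a 95% CI for the mean as the general rule for continuous variables. It then says that geometric statistics "will also be presented in the descriptive statistics for the PK concentration data and PK parameters of" PSL, CBD and their metabolites. PD is not named.
- Protocol 9.4 says that all PD parameters, including changes, "will be listed and summarized by study part and treatment with mean, median, standard deviation (SD), minimum and maximum for the PD-PPS". It plans no geometric statistics.

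SAP 3.9, which lists departures from the protocol's analyses, does not mention adding geometric statistics for PD.

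**The concern.** A geometric mean, a geometric CV and a lognormal interval all need logarithms, and a change from baseline is often zero or negative. A programmer who follows SAP 10.1.1 literally must either leave those cells blank or let the software discard every value at or below zero. The second route yields a figure that describes only the participants whose score rose, printed beside an arithmetic mean based on everyone. Smooth pursuit, the Part A primary endpoint (SAP 2.1.1), is among the variables covered.

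The list matches the one that SAP 9.1.1 gives for PK concentrations and parameters. That suggests PK text carried over to PD rather than a deliberate choice, though the documents do not say so. SAP 3.1 assigns the PD outputs to the sponsor and the other outputs to the CRO, so the PD programmers would have to settle the matter themselves.

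**Working it through.** **1. The plan's own figure.** There is none to reproduce; the SAP gives no numerical result for these tables. The check is by definition, followed by an illustration of size.

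**2. Definitions.** With s the SD of log x:
- geometric mean = exp(mean of log x)
- geometric CV (%) = sqrt(exp(s²) - 1) × 100 (SAP 4.2.1)
- lognormal 95% CI = exp(mean of log x ± t × s / sqrt(n))

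All three need every x > 0. A change is post-baseline minus baseline, so x can be negative, zero or positive.

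**3. Is there a rule that rescues the calculation?** The half-LLOQ substitution in SAP 4.2.1 is for PK concentrations, and SAP 4.2.2 extends it to safety laboratory data. Neither covers PD. SAP Appendix 14.1 adds 2 to each Bowdle item before taking logs in the two composites, which keeps the log defined at a score of 0. SAP 10.1.1 has no comparable step.

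**4. Inputs for the illustration.** n = 22 is the planned number of evaluable participants in Part A (SAP 2.3). The mean changes (0, ±3.96, -8) and SDs (4, 6, 8 percentage points) are assumptions. The values 3.96 and 6.0 are borrowed from SAP 2.3 for scale only. There they are a detectable ethanol effect and the SD of a paired treatment difference, not quantities for change from baseline, for which the documents give no SD. Changes are taken as normal.

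**5. Formulas.** Share positive: p = Phi(mean/SD). Expected usable values: 22p. Probability that all 22 are usable: p^22. The geometric mean of the positive values is the median over 20,000 simulated samples of 22.

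Example: mean -3.96, SD 6 gives p = Phi(-0.66) = 0.255, so 22 × 0.255 = 5.6 usable values and 1 - 0.255 = 74.5% unusable.

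| Mean change | SD | Share positive | Usable of 22 | P(all 22 usable) | Geometric mean of positives |
|---|---|---|---|---|---|
| 0 | 6 | 0.500 | 11.0 | 2.4e-7 | +3.3 |
| -3.96 | 4 | 0.161 | 3.5 | 3.6e-18 | +1.4 |
| -3.96 | 6 | 0.255 | 5.6 | 8.5e-14 | +2.4 |
| -3.96 | 8 | 0.310 | 6.8 | 6.6e-12 | +3.4 |
| -8 | 6 | 0.091 | 2.0 | 1.3e-23 | +1.9 |
| +3.96 | 6 | 0.745 | 16.4 | 1.6e-3 | +4.8 |

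At a mean change of -8 with SD 6, 39% of samples have fewer than two positive values (11% with SD 8, 91% with SD 4), so no geometric CV or interval could be formed even after discarding values. The last row shows that a score expected to rise does not escape: all 22 changes are positive in only 0.16% of samples, and the geometric mean of the positives exceeds the true mean.

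**6. Absolute values.** The alcohol VAS is presented raw (SAP 10) on a line that starts at sober (Protocol 8.7.1), and the feeling-high item needs no derivation (SAP Appendix 14.1). Both can be exactly 0. The Bowdle composites cannot: each averages log10(item + 2), so the minimum is log10(2) = 0.30. Their changes from baseline can still be zero or negative.

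**The case against.** The strongest reply is that little in the report depends on these cells, and most of it stands.

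- A reader might infer that the change tables for the primary endpoint would be empty or built wholly from a biased subset. The documents do not support that: the same sentence in SAP 10.1.1 also plans n, arithmetic mean, median, SD, minimum and maximum, all computable from every observation.
- A reader might infer that no valid interval is planned. SAP 3.1 already provides a 95% CI for the mean as the general rule, and SAP 10.1.1 also plots least squares means with 95% intervals. What is true is narrower: the specific list in 10.1.1 omits the arithmetic interval and puts a lognormal one in its place.
- A reader might infer that the primary conclusion is at risk. It is not. The comparison of PSL plus ethanol with PSL plus placebo is a model contrast with a 95% CI (SAP 10.1.2 and 10.1.2.1), initially on untransformed values, and uses none of the geometric descriptives.
- Not every PD change is expected to fall. Intoxication raises the alcohol VAS, and the Bond-Lader alertness items run from alert to drowsy, so sedation raises those scores before any inversion. This limits any statement about direction, but a single value at or below zero is enough to break the calculation.
- Geometric summaries are legitimate for strictly positive absolute values. The remedy therefore need not remove them from every PD table.

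None of this makes the geometric statistics computable for changes, and no rule in the plan resolves the clash with SAP 3.1 and Protocol 9.4.

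**Conclusion.** Wrong as written; minor, and confined to descriptive tables. That the geometric mean, geometric CV and lognormal interval are undefined for PD changes at or below zero follows from the SAP's own definitions and needs no assumption. The same holds for absolute scores of 0 on the untransformed VAS items.

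The size is illustrative and rests on assumed normal changes, n = 22 and assumed means and SDs. With SD 6, about half the values are unusable at no mean change and about three quarters at -3.96. There, discarding the unusable values would print a geometric mean of roughly +2.4 beside an arithmetic mean near -4. The wrong sign persists for SDs from 4 to 8. Arithmetic summaries and primary inference are unaffected.

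**What to change.** In SAP 10.1.1, delete the geometric mean, geometric CV and lognormal CI for PD changes from baseline and for any PD score that can be 0. For these, report n, arithmetic mean, SD, median, minimum, maximum and the 95% CI for the arithmetic mean, in line with SAP 3.1. Geometric statistics may stay for strictly positive absolute PD values if the sponsor wants them; in that case, add the choice to SAP 3.9 as a departure from Protocol 9.4.

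The cost is one sentence in the SAP and the matching edit to the PD table shells. SAP 1 requires an amendment for changes to analysis definitions before database lock, so it can go into the next one. No data collection, sample size or model changes.

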10.1.2 Statistical analysis of pharmacodynamics variables

For the analysis of PD variables, there will be two baselines per study participant (Kenward-Rogers, 2010):

1. Between subject baseline = mean of all predose PD parameter for each subject
2. Within subject baseline = baseline at given day – between subject baseline

The PD parameters will be analyzed separately by a repeated measures ANOVA with treatment, time, treatment by time, period and sequence as fixed effects; time as repeated measure; with subject by period and subject as random effects and within subject baseline and between subject baseline and the baseline interactions with time as covariates. [Section 10.1.2.1](#) and [Section 10.1.2.2](#) specify which treatments to include in the model.

Due to the confounding of treatment within period within the design only the periods of interest will be included in any given comparison. For example, if the comparison is within the interaction phase then only Periods 4 and 5 will be kept in the model.

Period should be removed from the model statement due to confounding with treatment in any comparisons where either test or reference period only contains one treatment option. It will be left in the repeated statement as period is synonymous with treatment.

The following SAS code may be used for the repeated measures ANOVA stated above:

Contrasts for each PD variable will be reported along with 95% CI. Variables will initially be analyzed without transformation, but if visual inspection of the residual plots suggest otherwise (data are not normally distributed), an appropriate transformation may be applied.

Further exploratory analyses for PD variables may be conducted by UCB.

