10.1.2.2 CBD and PSL (Part B)

The similarity of the PD parameters between treatment will be analyzed using the model specified in [Section 10.1.2](#), where treatment includes CBD, PSL, CBD+PSL and CBD+Placebo.

The following contrasts will be calculated within the model:

- CBD+PSL (Treatment Period 4/5: Day 5) vs PSL (Treatment Period 2: Day 5) (primary comparison)
- CBD+PSL (Treatment Period 4/5: Day 5) vs CBD (Treatment Period 3: Day 16)
- CBD+PSL (Treatment Period 4/5: Day 5) vs CBD+Placebo (Treatment Period 4/5: Day 5)

This analysis will also be performed for PD variables measured in Treatment Period 4/5, Day 1. Any treatment effect may be compounded by time in the first and second comparison stated above. Additionally, there may be a learning effect due to study participants performing the PD assessments multiple times.

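### In the randomised Part B Day 5 PD contrast CBD+PSL vs CBD+Placebo, the given-day baseline follows four days of PSL in one condition only, so adjusting for it can shrink the estimated effect

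*SAP*

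**What the plan says.** SAP 10.1.2 puts two baselines in the PD model. One is a participant's mean over all predose values. The other is "Within subject baseline = baseline at given day – between subject baseline". The model takes "within subject baseline and between subject baseline and the baseline interactions with time as covariates". For the descriptive output, SAP 3.3 (Table 3-1) says that "baseline for change from baseline summaries and tables is defined as the average of the two values measured at predose of given day". For Day 5 data, both rules point to Day 5 predose.

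SAP 10.1.2.2 lists three Part B contrasts. The third is "CBD+PSL (Treatment Period 4/5: Day 5) vs CBD+Placebo (Treatment Period 4/5: Day 5"). Its two conditions are the randomised crossover of Treatment Periods 4 and 5. SAP 10.1.2 says that "if the comparison is within the interaction phase then only Periods 4 and 5 will be kept in the model", so this contrast also keeps its period term. Of the other two the SAP warns: "Any treatment effect may be compounded by time in the first and second comparison stated above". It adds that "there may be a learning effect due to study participants performing the PD assessments multiple times".

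Protocol Table 1-8 (footnote d) gives PSL twice daily on Days 1 to 4, before the Day 5 morning dose. The same table schedules NeuroCart on Days 1 and 5 of both periods, and footnote h asks for two predose runs. The SAP already plans to use the Day 1 data: "This analysis will also be performed for PD variables measured in Treatment Period 4/5, Day 1".

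**The concern.** A baseline covariate in a randomised comparison should be measured before the treatments diverge. Here Day 5 predose follows eight PSL doses (four days, twice daily) in the PSL period and none in the placebo period. If some PSL effect is still present at that trough, the covariate carries part of the effect being estimated, and adjusting for it removes that part. The loss is toward no effect, in an analysis that SAP 10.1.2.2 frames as one of similarity.

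This is the only randomised contrast among the three in Part B, so it is the one least exposed to time and learning. The stated objective (SAP 2.1.2) is the PD interaction at steady state, and Protocol 4.2.2 places assessments after four days of dosing for that reason. In addition, the model subtracts a fraction of the predose difference while the change-from-baseline tables subtract all of it, so the two outputs can disagree on the same data.

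**Working it through.** **The plan's own figure.** SAP 2.3 gives n = 22, difference 3.96, SD of difference 6.0, two-sided 0.05, paired t-test, 80% power. The noncentral t distribution gives 79.95% at n = 20 and 83.9% at n = 22. The stated size is reproduced to within two participants, on the safe side. That calculation concerns ethanol and the CBD effect. The documents give no effect size or SD for the contrast at issue, so 3.96 and 6.0 serve below only as a borrowed scale.

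**Algebra.** Let E be the Day 5 post-dose difference, f the share of E present at Day 5 predose, and b the within-subject baseline slope. The between-subject baseline is constant within a participant and cancels.

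- Model: E - b × fE = E(1 - bf)
- Change-from-baseline tables (b = 1): E(1 - f)

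Because the model includes baseline-by-time terms, b and hence the loss can differ by timepoint.

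**Numbers at E = 3.96.** The values of b and f are assumptions; for example 3.96 × (1 - 0.5 × 0.5) = 2.97.

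| f | Model, b=0.4 | Model, b=0.5 | Model, b=0.7 | Tables |
|---|---|---|---|---|
| 0 | 3.96 | 3.96 | 3.96 | 3.96 |
| 0.25 | 3.56 | 3.46 | 3.27 | 2.97 |
| 0.5 | 3.17 | 2.97 | 2.57 | 1.98 |
| 1 | 2.38 | 1.98 | 1.19 | 0 |

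**Simulation.** A 2x2 crossover was simulated with 22 participants (11 per sequence) and 20,000 replicates per setting. Post-dose within-period variance was 18, so the SD of the difference is √(2 × 18) = 6.0. Variances for period, day and baseline noise were (3,3,9), (4,5,9) and (5,9,6). These give b = 6/15 = 0.4, 9/18 = 0.5 and 14/20 = 0.7. Same-day estimates agreed with the formula to within 0.02. The Day 1 baseline averaged 3.94 to 3.98 in every setting, and omitting the term was likewise unbiased. There was one post-dose outcome, so the full repeated-measures model was not simulated.

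Root mean squared error around E = 3.96, for b = 0.4 / 0.5 / 0.7:

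| f | Same-day baseline | Day 1 baseline | Coverage of same-day 95% CI |
|---|---|---|---|
| 0 | 1.23 / 1.14 / 0.88 | 1.30 / 1.28 / 1.27 | 95% |
| 0.25 | 1.32 / 1.25 / 1.13 | 1.30 / 1.28 / 1.28 | 94 / 93 / 89% |
| 0.5 | 1.53 / 1.56 / 1.68 | 1.28 / 1.28 / 1.26 | 91 / 88 / 70% |

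Coverage with the Day 1 baseline was about 95% throughout. At E = 3.96 the same-day model has similar or lower total error up to f of about 0.2 to 0.3, and higher error beyond.

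**Dependence on E.** The bias is b × fE, so only the product fE matters. At E = 1.98, f = 0.5 gives fE = 0.99, the same as f = 0.25 at E = 3.96. The middle row then applies, and the break-even moves to f of about 0.5 or higher.

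**The case against.** **The SAP was entitled to this choice.** Protocol 9.2 makes the last assessment before dosing the default baseline and leaves specific baselines to the SAP. Protocol 8.7 mentions Day 1 predose but does not say of each Treatment Period. A reader might infer that the SAP contradicts the protocol; the documents do not support that. This is an analysis choice.

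**Little hangs on the contrast.** Part B's primary endpoints are PK, and its labelled primary PD comparison is CBD+PSL vs PSL. No acceptance range is set for PD. SAP 10 and 10.1.1 also summarise absolute values, which show the full Day 5 difference. All of this stands and limits the weight of the point, although it does not repair the model estimate.

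**The same-day covariate may be the better one.** If little persists to trough, it is more precise and has lower total error. This stands, and the documents do not say how much persists.

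**Perhaps only the increment after the morning dose is wanted.** The SAP does not say so, and the steady-state objective points the other way. Even for that target, E(1 - f), the model agrees with the tables only when b = 1 or f = 0.

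**Replacing the tables would do harm.** Moving them to Day 1 would put CBD+PSL on a different basis from PSL in Treatment Period 2 and CBD in Treatment Period 3. This stands; those tables should be kept.

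**The fixed-order contrasts.** A reader might infer that they need the same change. There the same-day value also absorbs part of the learning drift the SAP expects. The drift is unknown, so the documents do not show either choice to be better.

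**Conclusion.** The concern holds for one contrast. In the Day 5 comparison of CBD+PSL with CBD+Placebo, the planned model adjusts for a post-treatment value and estimates E(1 - bf). The bias is toward no effect when b and f are positive, and zero if nothing persists to predose. At b = f = 0.5 the attenuation is 0.5 × 0.5 = 25% in the model and 50% in the tables. These sizes are illustrative because the documents give neither b nor f; coverage and the error break-even also depend on a borrowed E.

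The Day 1 alternative assumes that no PSL effect remains at Day 1 predose of Treatment Period 5 in those who had PSL first. Protocol Table 1-8 provides a PSL washout of at least 4 days there.

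A reader might infer that the Part B PD results are unreliable as a whole, or that the stated power is lost. Neither follows. The endpoints are secondary or other, absolute-value summaries are unaffected, no power is stated for this contrast, and no primary analysis or decision rule changes. It is worth fixing because the remedy is cheap and uses data already scheduled.

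**What to change.** Before unblinding, for this one contrast:

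- In the model, replace the Day 5 predose value with the mean of the duplicate Day 1 predose NeuroCart values of the same Treatment Period (4 or 5), or drop the same-day within-subject term.
- State that the target is the full on-treatment difference at PSL steady state.
- Keep the same-day-adjusted estimate as a sensitivity analysis.
- Keep the given-day change-from-baseline tables, and add change from Day 1 predose for Treatment Period 4/5 Day 5.
- Apply this to the NeuroCart tests that Protocol Table 1-8 lists for Part B. Adaptive tracking is not in that list, so no Day 1 value is evident for it.

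No change is required for the fixed-order contrasts, the Part A primary contrast, Ethanol vs Placebo, or the Treatment Period 4/5 Day 1 analysis.

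The cost is SAP wording and programming, with no new visits. If nothing persists to predose, precision falls: in the illustration the standard error rises from about 0.9–1.2 to about 1.3. The Day 1 baseline is no more precise than omitting the term; its use is to give the model and the added tables one common baseline taken before that period's PSL.
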